**Table 10–12: Potential drug-induced liver injury laboratory measurements**

Virology-related	Hepatitis A IgM antibody
	HBsAg
	Hepatitis E IgM antibody
	HBcAb-IgM
	Hepatitis C RNA
	Cytomegalovirus IgM antibody
	Epstein-Barr viral capsid antigen IgM antibody (if unavailable, obtain heterophil antibody or monospot testing)
Immunology	Anti-nuclear antibody (qualitative and quantitative)
	Anti-smooth muscle antibody (qualitative and quantitative)
	Type 1 anti-liver kidney microsomal antibodies (qualitative and quantitative)
Hematology	Eosinophil count
Urinalysis	Toxicology screen a
Chemistry	Amylase
	ALT, AST
	If total bilirubin $\geq 1.5 \times \text{ULN}$ , obtain fractionated bilirubin to obtain % direct bilirubin
	Serum CPK and LDH to evaluate possible muscle injury causing transaminase elevation
Additional	Prothrombin time/INR b
	Serum pregnancy test
	PK sample

**Table 10–12: Potential drug-induced liver injury laboratory measurements**

ALT=alanine aminotransferase; AST=aspartate aminotransferase; CPK=creatine phosphokinase; HBcAb-IgM=hepatitis B core antibody-IgM; HBsAg=hepatitis B surface antigen; IgM=immunoglobulin M; INR=international normalized ratio; LDH=lactate dehydrogenase; PDILI=potential drug-induced liver injury; PK=pharmacokinetic; RNA=ribonucleic acid; ULN=upper limit of normal

a For detecting substances (ie, amphetamines, benzodiazepines, opioids, marijuana, cocaine, phencyclidine, and tricyclic antidepressants), additional tests may be performed based on the Investigator’s medical judgment and patient’s history.

b Measured only for subjects with ALT >8xULN, elevations in total bilirubin, and symptoms of hepatitis or hypersensitivity. Hepatitis symptoms include fatigue, nausea, vomiting, and right upper quadrant pain or tenderness; hypersensitivity symptoms include eosinophilia (>5%), rash, and fever (without clear alternative cause).

## 10.5 Vital signs and other observations related to safety

### 10.5.1 Vital signs

The following vital signs measurements will be assessed:

- Systolic blood pressure (mmHg).
- Diastolic blood pressure (mmHg).
- Pulse rate (bpm).
- Temperature (°C).
- Body weight (kg)

The following summaries will be provided:

- A summary of the absolute and change from PA0008 Baseline for each vital sign variable at each visit, by treatment group at the completion of PA0008 and overall.
  - This summary will include the derived BMI at each time point.
- A summary of the number and percentage of subjects experiencing at least 1 on-treatment markedly abnormal value, as defined in Table 10–13, for a vital sign variable during the Treatment Period (excluding any measurements that occurred prior to the first administration of study medication in PA0009 or more than 140 days after the last administration of study medication) by treatment group at the completion of PA0008 and overall (based on change from PA0008 Baseline).

**Table 10–13: Definitions of markedly abnormal blood pressure values**

Variable (Unit)	Markedly abnormal low	Markedly abnormal high
Systolic blood pressure (mmHg)	<90 and a decrease from PA0008 Baseline of $\geq 20$	>180 and an increase from PA0008 Baseline of $\geq 20$
Diastolic blood pressure (mmHg)	<50 and a decrease from PA0008 Baseline of $\geq 15$	>105 and an increase from PA0008 Baseline of $\geq 15$

Vital signs measurements, including age, sex, race, weight, and flags to identify markedly abnormal values, will be listed. The listing will include the derived BMI at each time point.

## 10.5.2 Electrocardiograms

A summary of the number and percentage of subjects with normal, abnormal not clinically significant, and abnormal clinically significant ECG results by visit will be presented by treatment group at completion of PA0008 and overall.

The following ECG variables will be summarized by visit (absolute values and change from PA0008 Baseline), by treatment group at completion of PA0008 and overall:

- QTcF interval (ms)
- QTcB interval (ms)
- RR interval (ms)
- PR interval (ms)
- QRS duration (ms)
- QT interval (ms)

Outliers in QTcF and QTcB are defined as values meeting the following criteria at any time in PA0009:

- QTcF or QTcB >450 ms OR
- QTcF or QTcB change from PA0008 Baseline >30 ms

Outliers will be summarized using the following categories:

- Values >450 ms, >480 ms and >500 ms
- Increase from PA0008 Baseline of >30 ms, >60 ms and >90 ms
- Value >450 ms AND increase from PA0008 Baseline of >30 ms
- Value >500 ms AND increase from PA0008 Baseline of >60 ms

The summary will include the number and percentage of subjects who meet the criteria above at any on-treatment (scheduled or unscheduled) assessment (excluding any measurements that occurred prior to the first administration of study medication in PA0009 or more than 140 days after the last administration of study medication).

All ECG variables will be listed. A separate listing of ECG findings will be presented together with the interpretation (normal, abnormal not clinically significant, or abnormal clinically significant).

## 10.5.3 Other safety variables

### Assessment of Tuberculosis

[figure not shown]
Scheduled TB laboratory test results will be included in the laboratory data listings. Results of unscheduled TB testing at local laboratories will be listed separately. The response to the first question of the 'Evaluation of signs and symptoms of tuberculosis' questionnaire data will be listed.

---

[figure not shown]
## Electronic Columbia Suicide Severity Rating Scale

The electronic Columbia-Suicide Severity Rating Scale (eC-SSRS) is a standardized and validated instrument developed for the assessment of the severity and frequency of suicidal ideation and behavior (Posner et al, 2011; Mundt et al, 2010).

Suicidal ideation is defined as an event in any of the following 5 categories:

Suicidal behavior is defined as an event in any of the following 4 categories:

Suicidal ideation or behavior is defined as an event in any of the above 9 categories.

Self-injurious behavior without suicidal intent will also be reported.

The eC-SSRS can be administered to assess suicidal ideation and behavior over a lifetime, or since the last time it was assessed. The intent in this OLE study was to assess suicidal ideation and behavior since the last time it was assessed and refer back to the lifetime assessment conducted at the start of PA0008. However, some subjects completed the 'lifetime' assessment (in error) at one or more visits in PA0009 and recorded positive responses to some questions. Based on a review of their original lifetime assessment in PA0008, these positive responses are not considered to represent a change in suicidal ideation and behavior during the study. The summary tables will include only the 'since last assessment' responses; all responses will be listed.

The incidence of subjects with suicidal ideation, suicidal behavior, suicidal ideation or behavior and self-injurious behavior at any on-treatment assessment (excluding any measurements that occurred prior to the first administration of study medication in PA0009 or more than 140 days after the last administration of study medication), will be summarized by treatment group at completion of PA0008.

eC-SSRS data will be listed.

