## 2.4 Determination of sample size

There is no formal sample size calculation for this study. The sample size is determined by the number of subjects eligible for PA0009 and rolling over from PA0008. Up to 200 subjects from PA0008 could be enrolled into this study.

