Descriptive statistics will be displayed to provide an overview of the study results. For categorical variables, the number and percentage of subjects in each category will be presented. The denominator for percentages will be based on the number of subjects included in the respective analysis set. For observed case (OC) summaries, or summaries of data where no imputation is made for missing data, subjects with missing data will be accounted for by including a “Missing” category (corresponding to subjects with missing data for the variable being summarized) as the last row in the list of categories being summarized. Percentages will be presented to 1 decimal place. If the percentage is 100%, no decimal will be presented. If the percentage is 0, no percentage will be presented. The % sign will be presented in the column header, but not with each individual value.

For continuous variables, descriptive statistics will include number of subjects with available measurements (n), mean, standard deviation (SD), median, minimum, and maximum. Decimal places for descriptive statistics will apply the following rules:

- “n” will be an integer.
- Arithmetic and geometric mean, SD, and median will use 1 additional decimal place compared to the original data.

- Coefficient of variation (CV [%]) will be presented with 1 decimal place.
- Minimum and maximum will have the same number of decimal places as the original value.

The number of decimal places used for derived efficacy variables is shown in [Table 3-1](#).

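### SAP 10.5.3 rests its 'no change' conclusion on repeat lifetime 'yes' answers to the eC-SSRS, which cannot separate past history from recurrence

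*SAP*

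**What the plan says.** SAP 10.5.3 explains that PA0009 was meant to cover suicidality "since the last time it was assessed and refer back to the lifetime assessment conducted at the start of PA0008". It then discloses that "some subjects completed the 'lifetime' assessment (in error) at one or more visits in PA0009 and recorded positive responses to some questions". The ground for setting these answers aside is given in one clause: "Based on a review of their original lifetime assessment in PA0008". No other source is named. The conclusion is that "these positive responses are not considered to represent a change in suicidal ideation and behavior during the study".

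The handling rule follows: "The summary tables will include only the 'since last assessment' responses; all responses will be listed". The tables report the incidence of subjects with ideation, behavior, either of these, or self-injurious behavior at any on-treatment assessment.

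SAP 3.1 sets the general denominator: "The denominator for percentages will be based on the number of subjects included in the respective analysis set". It also adds a 'Missing' category to summaries in which missing data are not imputed. SAP 10.5.3 does not say how a visit with only a lifetime form is treated. It gives no count of affected subjects or visits and no sensitivity analysis.

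**The concern.** The lifetime question never resets. A subject who truthfully reported ideation before PA0008 must answer 'yes' at every later lifetime assessment, whatever happened in between. Agreement between the two lifetime forms is therefore expected with or without a new event, and it is weak ground for a statement about the study period.

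The primary objective of PA0009 is long-term safety (Protocol 3.1), and suicidal ideation and behavior is a prespecified safety topic (Protocol 9.1.3). Protocol 9.6.7 gives the scale the job of capturing what may occur during the study. By the SAP's own reasoning, the affected subjects have a positive lifetime history. At stake is whether the eC-SSRS table can be read as showing no on-study ideation or behavior in these subjects, or only that none was captured on the correct form.

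**Working it through.** The documents state no figure for this point, so there is nothing to reproduce. The check has four steps.

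**1. What the comparison of forms can show.** For one item, assuming truthful and consistent answers:

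| Lifetime item at PA0008 start | New event since then | Lifetime item at PA0009 visit | What the comparison shows |
|---|---|---|---|
| no | no | no | event excluded |
| no | yes | yes | change detected |
| yes | no | yes | cannot tell |
| yes | yes | yes | cannot tell |

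In the last two rows the probability of a PA0009 'yes' is 1 with or without recurrence. The likelihood ratio is 1/1 = 1, and the answer carries no information about recurrence. The problem is confined to repeat positives on items already endorsed. A lifetime 'no' and a newly endorsed item are both informative.

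**2. How long an interval is affected.** Protocol Table 5-1 schedules the eC-SSRS at entry, Weeks 4, 8, 12, 24, 36, 48, 60, 72, 84, 96, 100 and 104, and at the safety follow-up visit. For a subject who completes treatment, that visit falls at Week 100 + 20 = 120. These 14 time points give 13 intervals:

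- 4 weeks: five (ending at Weeks 4, 8, 12, 100 and 104); 4/120 = 3.3%
- 12 weeks: seven (ending at Weeks 24 to 96); 12/120 = 10.0%
- 16 weeks: one (Week 104 to safety follow-up); 16/120 = 13.3%

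Check: 5×4 + 7×12 + 1×16 = 120 weeks. One repeat-positive lifetime form thus leaves 4 to 16 weeks without a usable eC-SSRS result in the summary. This assumes that the next correct form looks back only to the erroneous visit. The documents do not say how the device sets its reference point after a wrong-version form.

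**3. How an affected subject is counted.** Only since-last-assessment responses enter the numerator (SAP 10.5.3), and the denominator is the analysis set (SAP 3.1). A subject with one repeat-positive lifetime form and otherwise negative correct forms stays in the denominator, adds nothing to the numerator and has data, so does not belong in the 'Missing' row. A subject with no correct form at all might fall in that row. With the denominator unchanged, dropping positive answers can lower the incidence or leave it as it is, but cannot raise it.

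**4. Possible size.** SAP 2.4 gives the maximum N: "Up to 200 subjects from PA0008 could be enrolled into this study". The number of indeterminate subjects, k, is not in the documents; I assume 1 to 10. With x tabulated events, the incidence lies between x/N and (x + k)/N, a width of k/N, or 1/200 = 0.5 percentage points per subject. For x = 0, with exact two-sided 95% upper limits (for 0/200, 1 − 0.025^(1/200) = 1.83%):

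| k | As tabulated, 0/200 | Indeterminate excluded, 0/(200 − k) | All counted as events, k/200 |
|---|---|---|---|
| 1 | 0% (upper 1.83%) | 0% (upper 1.84%) | 0.5% (upper 2.75%) |
| 5 | 0% (upper 1.83%) | 0% (upper 1.87%) | 2.5% (upper 5.74%) |
| 10 | 0% (upper 1.83%) | 0% (upper 1.92%) | 5.0% (upper 9.00%) |

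Removing the indeterminate subjects from the denominator hardly moves the result. What matters is whether they are visible. The last column is a ceiling, not an estimate.

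**The case against.** The strongest reply is that the SAP is open about the error, keeps every response in the listings, and has other routes to the same information. Adverse events are prompted at each study visit (Protocol 9.1.4). An external committee adjudicates potential neuropsychiatric events for suicidal ideation and behavior, with its own table and listings (SAP 10.2.3). The eC-SSRS incidence is not among the primary, secondary or other safety variables in Protocol section 4 or SAP 2.2.1, and the study is descriptive. The scale also grades severity and frequency, and the item categories cannot be read in the public copy, so the review may have compared more than yes or no; a step up in category would have shown.

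Most of this stands, and it rules out two stronger readings. A reader might infer that the SAP scores these visits as negative. It does not say so; non-event status is the subject-level effect of two rules taken together. A reader might also infer that the interval is never assessed. That is wrong: a lifetime 'no' excludes an event, and adverse event collection and adjudication continue throughout.

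The reply does not rescue the conclusion itself. The adverse event prompt is a general health question. Nothing in SAP 10.2.3 or 10.5.3 says that these eC-SSRS positives were referred to the committee. The only evidence cited for 'no change' is the PA0008 lifetime form, which cannot detect recurrence at a level already endorsed.

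**Conclusion.** The concern holds in a limited form. For items already positive on the PA0008 lifetime form, the statement of no change during the study is not supported by the evidence cited for it, and the affected interval has no usable eC-SSRS result in the summary. The tabulated incidence may be understated and is not overstated by this rule. It would go too far to say that it must be too low: if nobody recurred, it is correct.

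The size cannot be determined. The bounds above rest on an assumed count of 1 to 10 subjects, N = 200, no tabulated events and truthful answers; the interval lengths assume the planned schedule. This is a cheap improvement to a safety display and does not undermine the study's safety conclusions.

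**What to change.** In SAP 10.5.3:

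1. Report how many subjects and visits had a lifetime form in error. Show subjects with a repeat-positive lifetime response and no valid since-last-assessment response for that interval in a separate 'indeterminate' row, and state the denominator.
2. Limit the 'no change' statement to subjects for whom other source records, adverse event data or adjudication results exclude recurrence.
3. Optionally, add a sensitivity row that counts the indeterminate subjects as events. Label it an upper bound, because it may count history from before the study as on-treatment events.

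Steps 1 and 3 use data already collected and add at most two table rows. Step 2 changes one sentence and needs a cross-check against existing records. The price is a display that may look slightly less favourable.

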### Health Care Provider Consultations

Out-patient non-protocol health care provider consultations will be listed.

### Extra-articular assessments

Extra-articular assessments performed after the PA0009 EV will be listed separately for the SS.

#### **10.5.4 Comments**

A listing of comments will be presented, based on the ES. This listing will include comments received from the laboratory vendors (including safety laboratory data, PK data, and ADAb data).

This document cannot be used to support any marketing authorization application and any extensions or variations thereof.

REDACTED COPY

## 12 APPENDIX

### 12.1 American College of Rheumatology Response Criteria

The rules for handling missing data in relation to defining the achievement of ACR20 response are provided in [Table 12-1](#). Similar rules will apply for the definition of ACR50 and ACR70. This table also indicates, where appropriate, the imputation as a nonresponder (DTYPE = WC) in the analysis datasets for the NRI analyses. For tables presented on OC data, the data selected will include all instances where DTYPE is not populated in the analysis datasets.

**Table 12-1: Handling Missing Data for American College of Rheumatology Response Criteria Derivation**

Components – Joint Counts	Other Components	Other Component Status	ACR	DTYPE
TJC and SJC both missing, or one is missing and the other improved $\geq 20\%$	3 or more components present	3 or more components $\geq 20\%$ improvement	N	WC
TJC and SJC both missing, or one is missing and the other improved $\geq 20\%$	5 components present	2 or fewer components $\geq 20\%$ improvement	N	
TJC and SJC both missing, or one is missing and the other improved $\geq 20\%$	4 components present	2 or more components $\geq 20\%$ improvement	N	WC
TJC and SJC both missing, or one is missing and the other improved $\geq 20\%$	4 components present	1 or no components $\geq 20\%$ improvement	N	
TJC and SJC both missing, or one is missing and the other improved $\geq 20\%$	3 components present	2 or 1 components $\geq 20\%$ improvement	N	WC
TJC and SJC both missing, or one is missing and the other improved $\geq 20\%$	3 components present	No components with improvement $\geq 20\%$	N	

**Table 12-1: Handling Missing Data for American College of Rheumatology Response Criteria Derivation**

Components – Joint Counts	Other Components	Other Component Status	ACR	DTYPE
TJC and SJC both missing, or one is missing and the other improved $\geq 20\%$	0, 1 or 2 components present	Any	N	WC
TJC or SJC missing and the component present did not improve $\geq 20\%$	Any or none	Any	N	
TJC and SJC present but one or fewer $\geq 20\%$ improvement	Any or none	Any	N	
TJC and SJC present and both $\geq 20\%$ improvement	All 5 components present	3 or more components $\geq 20\%$ improvement	Y	
		Fewer than 3 components $\geq 20\%$ improvement	N	
	4 components present	3 or more components $\geq 20\%$ improvement	Y	
		2 components $\geq 20\%$ improvement	N	WC
		1 or fewer components $\geq 20\%$ improvement	N	
	3 components present	3 components $\geq 20\%$ improvement	Y	
		2 or 1 components $\geq 20\%$ improvement	N	WC
		No components $\geq 20\%$ improvement	N	
	0, 1 or 2 components present	Any	N	WC

## 12.2 Minimal Disease Activity

The rules for handling missing data in relation to defining the achievement of MDA are provided in [Table 12-2](#). This table also indicates, where appropriate, the imputation as a nonresponder (DTYPE = WC [worst case]) in the analysis datasets for the NRI analyses. For tables presented on OC data, the data selected will include all instances where DTYPE is not populated in the analysis datasets.

**Table 12-2: Handling Missing Data for MDA Derivation**

Components	Component Status	MDA	DTYPE
All 7 components present	5 or more meet criteria for MDA	Y	
	Less than 5 meet criteria for MDA	N	
6 components present	5 or more meet criteria for MDA	Y	
	4 meet criteria for MDA	N	WC
	3 or fewer meet criteria for MDA	N	
5 components present	All meet criteria for MDA	Y	
	3 or 4 meet criteria for MDA	N	WC
	2 or fewer meet criteria for MDA	N	
4 components present	4, 3 or 2 meet criteria for MDA	N	WC
	1 or fewer meet criteria for MDA	N	
3 components present	Any meet criteria for MDA	N	WC
	None meet criteria for MDA	N	
0, 1 or 2 components present	Any	N	WC

## 12.3 Classification of the SF-36 questionnaire

The 8 different scores calculated from the SF-36 questionnaire are presented in [Table 12-3](#).

**Table 12–3: Classification of the SF-36 questionnaire**

	Scales
[REDACTED]	Physical Functioning
[REDACTED]	Role-Physical
[REDACTED]	Bodily Pain
[REDACTED]	General Health
[REDACTED]	Vitality
[REDACTED]	Social Functioning
[REDACTED]	Role-Emotional
[REDACTED]	Mental Health

## 12.4 Identification of Opportunistic infections

Opportunistic infections are identified based on a reference spreadsheet (OI - MedDRA V 19.0.xlsx)

### Identification Process

The two steps below outline two ways in which opportunistic infections (or potential opportunistic infections) can be identified: Step 1: Refer to column B of the spreadsheet which identifies the PTs to be classified as opportunistic infections using either a single 'x' or a double 'xx'.

- TEAEs which code to a PT flagged with a single 'x' need to also be serious in order to be considered an opportunistic infection.
- All TEAEs which code to a PT flagged with a double 'xx' are considered to be an opportunistic infection, regardless of seriousness.

Step 2: Refer to column C of the spreadsheet which identifies the PTs that need to be evaluated on a case-by-case basis by the study physician in order to determine whether or not it is an opportunistic infection. If Column C has a single 'x', then the corresponding preferred term should be flagged for case-by-case review by the study physician.

### Review Process

Opportunistic infections for a given study will be reviewed on the following occasions:

At quarterly Infectious Disease Committee (IDC) Meetings, listings will be produced for each study (see details below) and reviewed by the corresponding study physician ahead of the IDC Meeting. The IDC will then agree on the final adjudication for each potential opportunistic infection.

A final listing for opportunistic infections (in the format described below) will be produced and agreed upon between the study physician and the IDC prior to finalizing the database.

In each of the circumstances described above, the study programming team will produce an Excel listing that will be provided to the project lead statistician, project lead programmer, and to the study physician (who will subsequently provide it to the IDC). The Excel listing will contain the following columns (using the descriptions below as the column headings in the Excel listing):

- Study ID
- Unique Subject ID
- AE Term (Verbatim)
- AE Preferred Term
- AE System Organ Class
- AE High Level Term
- AE Low Level Term
- Date of Onset
- Outcome of Adverse Event

- Date of Outcome
- TEAE Flag
- Serious Adverse Event?
- Relationship to Study Medication
- Intensity
- Action Taken with IMP
- Opportunistic Infection – Automatic
- Opportunistic Infection – Manual Review
- Flag
- Data Cut Date
- Opportunistic Infection – Final Adjudication

Note the following about the final 5 variables in this listing:

Opportunistic Infection – Automatic: This is flagged as “Y” if the criteria for automatic selection as described in “Step 1” of the identification process are met.

Opportunistic Infection – Manual Review: This is flagged as “Y” if the criteria for case-by-case selection as described in “Step 2” of the identification process are met.

Flag – This has a value of either “NEW” or “OLD”. It is marked as “NEW” if the event is appearing for the first time in that run of the listing. Otherwise, if it has appeared previously, it is marked as “OLD”. Unique records are determined by USUBJID AESPID for purposes of identifying whether an event has been modified from a previous run.

Date – Only for cases where Flag is “NEW”, this field will be populated with the data cut date for that particular run of the listing.

Opportunistic Infection – Final Adjudication – For new events, this is always left blank by the programmers. It should be completed by the study physician/IDC for every event that appears in the listing. For events adjudicated as opportunistic, the field should be populated with a “Y”.

Following each review by the study physician and IDC, the Opportunistic Infection – Final Adjudication column will be completed (as described above), and the spreadsheets for each study will be returned to the study programming team via e-mail (coordinated by the IDC secretary). Then, for subsequent runs of the listing, the study programming teams will incorporate adjudications from previous runs.

